2. SPECIFIC AIMS AND OBJECTIVES

We propose to test the effects of exogenous ALLO in a well-characterized cohort of women with mild to severe depression presenting during early and late perimenopause. This project will use an experimental placebo-controlled, mechanistic trial to determine acute and durable effects of exogenous ALLO on behavioral, cognitive, circuit-level, physiological, and molecular processes centered on the Negative Valence Systems and Arousal and Regulatory Systems Domains of the Research Domain Criteria (RDoC) framework. We expect to uncover neurobiological mechanisms that underlie depression during early and late perimenopause via three aims:

Aim 1: To determine the impact of allopregnanolone on key behavioral and circuit-based processes that underlie depression in perimenopausal women.

Hypotheses: Compared to placebo, exogenous ALLO will improve the following: **1a) behavioral/cognitive** measures of rumination and attentional bias toward negatively valenced external stimuli; and **1b) neurocircuitry**, via resting-state connectivity underlying rumination and negative attentional bias within the default mode network and between the default mode and salience networks.

Aim 2: To determine the impact of allopregnanolone on key molecular and physiological processes that underlie depression by indexing markers of neuroprotection, peripheral inflammation, and sleep physiology in perimenopausal women.

Hypotheses: Compared to placebo, exogenous ALLO will improve the following: **2a) neuroprotection**, via circulating levels of brain-derived neurotrophic factor (BDNF), and levels of N-acetyl-aspartate (NAA) in the medial prefrontal cortex, measured with magnetic resonance spectroscopy; **2b) inflammation**, via circulating levels of pro-inflammatory molecules; and **2c) sleep physiology**, via EEG-derived wakefulness after sleep onset.

[figure not shown]
Exploratory Aim 3: To identify mediators and moderators of the impact of allopregnanolone on clinically-defined global measures of depression severity in perimenopausal women.

Exploratory Hypotheses: The magnitude of improvement in clinically-defined global measures of depression severity induced by exogenous ALLO will be: **3a) mediated** by changes in behavioral and circuit-based outcomes derived from Aim 1, and changes in neuroprotective, inflammatory, and sleep physiology outcomes derived from Aim 2; and **3b) moderated** by prior depression illness course and perimenopausal factors.

Alignment with the 2020 NIMH Strategic Plan for Research: To uncover behavioral and neurobiological mechanisms that underlie PeriDep, we will identify mechanisms targeted by exALLO (Aims 1 and 2) and evaluate the relationship of changes in these therapeutic targets (as mediators) and changes to depression symptom severity (Exploratory Aim 3). Using a clinically effective pharmacological probe (exALLO) with proven antidepressant action allows us to directly perturb systems to identify the mechanisms through which enALLO induces PeriDep.

We used the Research Domain Criteria (RDoC) Framework¹ to select key mechanistic targets in pathways believed to underlie depression, including behavioral, circuit-based, molecular, and physiological processes. Specifically, we will investigate constructs within Negative Valence Systems (NVS) and Arousal and Regulatory Systems (ARS).

Figure 1 illustrates our overarching theoretical model and the integration of our outcomes across our multiple levels of investigation. In this model, molecular mechanisms drive subsequent changes at the level of brain circuitry, physiology, and behavior, which together, result in the clinical syndrome of PeriDep. The figure shows that ALLO may act at any level within the model to influence depression outcomes in PeriDep.

NVS Behavioral Targets:

- 1) Rumination is focused attention on one's distress,² which contributes to depressed mood. Patients with MDD ruminate more frequently than healthy individuals.³ Rumination is a risk factor for development and maintenance of MDEs,² and is associated with MDEs and subthreshold depression in women during Peri,⁴ potentially due to diminished production of P4.
- 2) Attentional bias toward negative stimuli: Depressed patients display mood-congruent processing biases, with slower reaction times, less accuracy on tasks that use positively valanced stimuli, and heightened sensitivity to negative feedback. Similar to rumination, P4 is inversely related to negative attentional bias in midlife women, suggesting negative bias is a potential therapeutic target of exALLO.

NVS Circuit-based Targets: Neural networks implicated in rumination and negative attentional bias are themselves mechanistic targets.

- 1) DMN abnormal reactivity is linked to rumination, along with

2) abnormal connectivity between DMN and SN that also reflect biases in assignment of salience and failure to shift attention away from self-referential processes in depression. Convergent evidence, including our own,⁵ suggests effects of enALLO on function in intrinsic networks related to rumination and negative attentional bias.

NVS Molecular and Physiological Targets:

1) Neuroprotection shields against cellular damage by processes such as excitotoxicity, mitochondrial dysfunction, neuroinflammation, and neurotrophin dysregulation.^{6,7} Peri women exhibit evidence of decreased neuroprotection.^{53,71} SSRIs exert neuroprotective effects,^{8,9} upregulating serum enALLO levels in depressed patients¹⁰⁻¹² and increasing two key brain markers of neuronal health:

- a) brain-derived neurotrophic factor (BDNF),^{6,13} measured peripherally; and
- b) N-acetyl aspartate (NAA) levels,¹⁴⁻¹⁶ measured *in vivo* in the brain. enALLO boosts neuroprotection,¹⁷⁻¹⁹ increasing neuronal viability via improved mitochondrial energetics,²⁰ oxidative stress,²¹ apoptosis,^{19,21-23} and BDNF levels in cell and animal models.²⁴⁻²⁶

2) Inflammation: Peri is a pro-inflammatory reproductive stage,²⁷ with increased rates of new-onset autoimmune diseases [e.g., multiple sclerosis (MS)]. Inflammatory responses during Peri also correspond with changes in brain structure²⁸ and function.^{29,30} Inflammation plays an important role in depression across the lifespan,³¹ at least in some individuals,³² and may contribute to PeriDep.⁴ ALLO has anti-inflammatory effects in both preclinical and human studies.³³ ALLO's anti-inflammatory action is demonstrated by reduced central nervous system measures in MS patients,³⁴ and indirectly by an inverse relationship of the ALLO precursor P4 with TNF- α , IL-6, and CRP in PeriDep. These findings suggest inflammation may be a therapeutic target of exALLO.

ARS Physiological Targets: A multi-factorial mechanistic pathway links sleep disturbance to depression, including affect response,^{35,36} neurotransmission,^{37,38} and changes in brain connectivity associated with cognition and mood.

Mechanisms Linking Sleep to Depression: Sleep loss adversely affects function in intrinsic brain networks, including creating an imbalance in DMN activation and decreasing thalamocortical FC,^{39,40} effects that may extend to impaired arousal, information integration, and cognition. Sleep disturbance may exacerbate depression severity by adversely altering inflammation⁴¹ (e.g., increased CRP and IL-6 levels), which can be reversed by cognitive behavioral therapy for insomnia.

ALLO and Sleep: exALLO administration induces benzodiazepine-like effects on sleep, reducing time to onset of NREM sleep.⁴²

[figure not shown]
Impact: Despite evidence from preclinical models and clinical observational studies, there remains a significant gap in our understanding of behavioral and neurobiological mechanisms that drive PeriDep. Paralleling the postpartum period, P4 falls during Peri, potentially translating to a causal role for the P4 metabolite enALLO in PeriDep, similar to what has been observed in PPD. By applying an experimental therapeutic approach using a controlled mechanistic trial, we will directly interrogate key therapeutic targets of exALLO to identify the mechanisms through which ALLO exerts clinical benefits on mood. This protocol will determine how ALLO's effects on molecular mechanisms, brain circuitry, physiology, and behavior in NVS and ARS constructs relate to changes in depression severity to identify behavioral and neurobiological mechanisms that underlie PeriDep. Our novel approach will provide critical insights to guide future interventions using ALLO and similar agents while identifying key mechanistic targets that can be harnessed to develop novel treatment approaches for PeriDep.

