1. BACKGROUND AND SIGNIFICANCE

Perimenopausal Depression: Midlife women are burdened with depression risk that is at least partly attributed to changing reproductive steroid dynamics across a prolonged reproductive transition. Perimenopause (Peri) confers a specific period of risk in women for subthreshold depressive symptoms and major depressive episodes (MDEs).¹ Indeed, women are twice as likely to experience MDEs in Peri than in late premenopause.^{2,3} MDEs during Peri represent depression recurrence for most affected women, but 45%–68% of women without a history of major depressive disorder (MDD) develop at least subsyndromal depressive symptoms during Peri.¹ While less severe than MDE, subsyndromal depression also causes significant distress and impairs quality of life.^{4,5} Perimenopausal depression (PeriDep) encompassing MDEs and subthreshold depression is common in women.

PeriDep shares risk factors with depression occurring at other life stages,¹ but also has unique risk factors including hot flashes [or vasomotor symptoms (VMS)], depression during other reproductive transitions, and sleep disturbance. Sleep disturbance is both a symptom of and causal for depression.^{6–8} Sleep problems are prevalent among Peri women due to nocturnal VMS, which lead to increased time spent awake after sleep-onset (WASO), the most prominent Peri sleep problem.⁹ However, sleep-onset problems and shorter total sleep time can also occur.¹⁰ Selective association of PeriDep with nocturnal VMS⁹ suggests that mechanistic processes underlying VMS at night¹¹ are especially disruptive to mood in Peri women.

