- The 60-hour brexanolone vs placebo infusion will begin in the evening of the 2nd inpatient night and end on the last morning immediately preceding post-treatment assessments
- Safety assessments will be conducted daily throughout the infusion and inpatient stay
- 2 electroencephalography (EEG) recordings (one before infusion and one during the final night of the infusion)
- At least once daily assessments of rumination, attentional bias, psychomotor vigilance, mood state (POMS), and depressive symptoms (before and after the infusion)
- Daily blood draws (before and after the infusion). Blood will be collected to run assays, including brain derived neurotrophic factor (BDNF), inflammatory biomarkers, reproductive hormones, serum ALLO levels, and serum for future analyses.
- One urine collection at admission for HCG, one at morning void after first night for melatonin. If there happens to be overnight voiding on first night additional samples will be requested but there is no scheduled collection, it will only be done if the participant is awake to void on their own.

Optional post-admission MRI Visit: resting-state functional MRI (rfMRI) / magnetic resonance spectroscopy (MRS) scans (after the infusion)

Interim Follow-Up and Remote Visit: During the 1-month follow-up period after participants are discharged from the inpatient visit, participants will be asked to complete daily monitoring of their sleep, VMS, and menstrual cycle patterns.

One remote interim visit approximately 2 weeks after the inpatient visit will take place to monitor adverse events, administer the C-SSRS, and assess mood state (POMS) and depressive symptoms.

Follow-Up In-Person Visit: Approximately 30 days after treatment initiation, participants will have a final follow-up in-person visit, during which they will undergo:

- Adverse event and safety monitoring
- Optional rfMRI/MRS scanning procedures
- Behavioral assessments including depressive symptom severity, mood state (POMS), rumination, and attentional bias, psychomotor vigilance; and
- Blood draw for neuroprotective and inflammatory biomarkers, reproductive hormones, ALLO levels, and serum for future analyses.

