For all primary contrasts, effect sizes estimated from either previous reports or our own preliminary data were large ($d \geq 0.8$). Specifically, for **Aim 1**: the effect of progesterone on rumination assessed using MADRS Item 9 (Pessimistic Thoughts) and the Beck Depression Inventory (BDI) subscore from Items 5 and 8 (Guilt and Self-incrimination, respectively) were large (Cohen's $d > 0.95$), an effect size that is consistent with previously reported⁴⁸, effects of exogenous ALLO on depression symptom ratings using the HDRS-17 being large (Cohen's $d > 1$), as will be investigated in **Aim 3**. Progesterone's effects on attentional bias to negative stimuli as well as functional connectivity are estimated from our preliminary data to be large ($d > 1$). **Aim 2**: Progesterone's effects are estimated from our preliminary data to be large on both BDNF and the inflammation index (derived from CRP, TNF- α , and IL-6 levels) ($d \geq 0.8$). Effects of progesterone on NAA levels in the medial prefrontal cortex, estimated from our preliminary data, and EEG-derived WASO, estimated from a previous report⁴⁹ of exogenous progesterone on sleep parameters in postmenopausal women, are both large ($d > 1$). For Aim 3: Based on prior reports and our preliminary data, our sample size (n=80; 40 per arm) will yield more than 80% power to detect select mediation as identified above.

10. Monitoring and Quality Assurance

This mechanistic intervention study will be conducted as a single-site inpatient randomized placebo-controlled trial using an agent that is FDA approved for women with a hormonally based depression in a new population of women who also have a hormonally based depression. The dose and method of administration—60-hour infusion of brexanolone—will be identical to the marketed agent. Research participants will be closely monitored for adverse events by physicians and nurses in the CCI research unit and by our experienced investigative team, which together participated as a site for the Sage Therapeutics PPD Phase 2 clinical trials using SAGE-547 (now FDA-approved as brexanolone). To minimize risks during the infusion, the FDA-approved Risk Evaluation and Mitigation Strategy (REMS) for brexanolone¹ will be strictly adhered to by our hospital clinical staff on the IPM Unit, consistent with procedures we implemented during the SAGE-547 trial. Safety monitoring will include frequent nursing checks, continuous oxygen saturation by pulse oximetry monitoring, and

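### Aim 3 can credit WASO with mediating mood improvement when the drug has changed only sleep, because the plan does not separate sleep content or on-drug sedation from depression severity

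*Combined protocol and SAP*

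**What the plan says.** Section 2 sets Exploratory Aim 3 to find "mediators and moderators of the impact of allopregnanolone on clinically-defined global measures of depression severity". It names no scale. Hypothesis 3a lists as mediators the changes in Aim 1 outcomes "and changes in neuroprotective, inflammatory, and sleep physiology outcomes derived from Aim 2"; hypothesis 2c measures sleep physiology "via EEG-derived wakefulness after sleep onset".

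The scale appears in Section 9, where the effect-size paragraph cites "effects of exogenous ALLO on depression symptom ratings using the HDRS-17 being large" (d > 1) and says this will be investigated in Aim 3. The same paragraph puts the WASO effect at d > 1 and claims more than 80% power for selected mediation, without giving path coefficients.

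Section 6 schedules "2 electroencephalography (EEG) recordings (one before infusion and one during the final night of the infusion". Section 2 describes the drug's effect on sleep as benzodiazepine-like, and Section 7 gives sedation rates of 13–21% against 6% on placebo. Section 1 states: "Sleep disturbance is both a symptom of and causal for depression".

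For the mediation models, Section 9 plans bootstrapped indirect effects, PLS-SEM, and a predictor–criterion collinearity check at a variance inflation factor (VIF) of 3.3. It plans no depression score without sleep items and no analysis using sedation data. The Table of Procedures lists PROMIS-Depression, the Stanford Sleepiness Scale (SSS) and the Richmond scale (RASS), but none has a stated role in Aim 3.

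**The concern.** The plan itself gives sleep disturbance two roles: part of depression and cause of depression. A mediation claim concerns only the second. If the severity score includes sleep, a drug that merely helps women sleep through the night lowers WASO and the rated insomnia together. The mediator–outcome path is then non-zero even when mood, guilt and interest do not depend on sleep at all.

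The timing adds to this. The follow-up EEG is taken while the drug is running, so sedation may be a common cause of the mediator and of some ratings.

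Section 2 says the results should guide future interventions. A finding that WASO mediates the antidepressant effect would point to sleep as a treatment target. The design would support that reading only if the effect extended beyond the sleep content of the scale.

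**Working it through.** **The plan's own figure.** For d = 0.64 and 40 per arm, the noncentrality is 0.64 × √(40/2) = 2.86. Power is Φ(2.86 − 1.96) = 81.7% by the normal approximation and 80.7% by the noncentral t, so the stated figure of more than 80% reproduces. The mediation power cannot be checked, because no path coefficients or residual SDs are given.

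**Inputs from the documents.** 40 per arm; two-sided 5% per test; WASO effect d = 1 (stated as > 1).

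**Assumptions not in the documents.** The HDRS-17 form scores insomnia. SD of change is sS = 1.5–2 points for the sleep items and sR = 4–6 points for the other items. The drug effect on the other items is 3 points. Within arm, WASO correlates with the sleep items at r = 0.1–0.5 and with the other items not at all.

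**Model.** With T the treatment indicator and independent standard normal errors:
- WASO improvement: M = T + e₁
- Sleep items: S = sS × (r × M + √(1 − r²) × e₂)
- Other items: R = 3T + sR × e₃
- Outcome: S + R

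Mediation is called when both the treatment→WASO path and the WASO→outcome path (adjusted for treatment) are significant.

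- Treatment→WASO: power at d = 1 is 99.3%.
- WASO→outcome: the partial correlation is ρ = r × sS / √(sS² + sR²). The t noncentrality is ρ × √77 / √(1 − ρ²), with 77 degrees of freedom and critical value 1.99.
- Expected indirect effect: r × sS points. Its share of the total effect is r × sS / (3 + r × sS).

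Worked cell, r = 0.5, sS = 2, sR = 4: ρ = 1.0/√20 = 0.224; noncentrality 2.01; power 51.1%; × 0.993 = 50.8%.

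| r | lowest rate (sS 1.5, sR 6) | highest rate (sS 2, sR 4) | indirect effect, points | share of total effect |
|---|---|---|---|---|
| 0.1 | 5.5% | 6.7% | 0.15–0.20 | 5–6% |
| 0.2 | 7.0% | 12.1% | 0.30–0.40 | 9–12% |
| 0.3 | 9.6% | 21.5% | 0.45–0.60 | 13–17% |
| 0.5 | 18.4% | 50.8% | 0.75–1.00 | 20–25% |

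Simulation of the same model gave 5–7% at r = 0.1, 8–13% at 0.2 and 10–51% at 0.3–0.5. The one visible difference is the lower end at 0.2. There the formula and a 40,000-trial check of that cell both give 7%, so I quote 7–13%.

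With R alone as outcome the rate is 5%. That follows by construction, because the model makes R independent of WASO within arm. It is not evidence that the remedy works in real data.

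**Would the planned checks catch it?** VIF = 1/(1 − R²), so 3.3 needs R² = 1 − 1/3.3 = 0.70, a correlation of about 0.83. In the worst cell, over both arms:
- var(M) = 1 + 0.25 = 1.25
- cov(M, outcome) = 1.25 + 3 × 0.25 = 2.0
- var(outcome) = 1.25 + 3 + 2.25 + 1.5 + 16 = 24
- R² = 4/(1.25 × 24) = 0.13, so VIF = 1.15

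In 32,000 simulated trials the largest VIF was 1.9. The bootstrap removes a normality assumption. It estimates the same product of paths, whose expected value here is not zero.

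**The case against.** **Item content.** The documents do not list the HDRS-17 items. Section 1 calls sleep disturbance a symptom of depression, not an item of this scale. This stands: the point is conditional on the form used.

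**Size.** The correlation between one inpatient night of EEG and a rated insomnia score has no source in the documents, and at 0.1 the excess over 5% is trivial. This stands too. A reader might infer that overlap will be reported as mediation. The figures do not support that: only the most extreme cell reaches about half of trials, and the indirect effect is at most a quarter of the total, which would suggest partial mediation.

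**The mediator inside the outcome.** A reader might say WASO is literally part of the score. It is not. WASO is an EEG measure that shares a construct with sleep items. Nor is a sedative effect on WASO spurious: the treatment→WASO path is genuine, and only the WASO→depression path is in doubt.

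**Rumination.** A reader might extend the point to rumination, since Section 9 bases that effect size on "rumination assessed using MADRS Item 9 (Pessimistic Thoughts) and the Beck Depression Inventory (BDI) subscore from Items 5 and 8". But the trial measures rumination with the Ruminative Response Scale, and the documents give the items of neither that scale nor the HDRS-17. They do not establish an overlap.

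**Existing protection.** Aim 3 speaks of measures in the plural, PROMIS-Depression is collected, and a parallel 30-day model is planned, when acute sedation is an unlikely shared cause. This helps only in part. PROMIS-Depression has no assigned role, a 30-day total would still contain any sleep items, and the EEG is not repeated at day 30, so that model has no concurrent WASO.

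**Exploratory status.** No primary outcome, sample size or safety decision depends on Aim 3. This limits the severity but does not make the result interpretable.

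**Conclusion.** The gap is real and moderate. The plan tests WASO, recorded after baseline only under a sedating infusion, as a mediator of a severity score that probably includes sleep, and it has no step to tell a sleep effect from a mood effect. How often this misleads depends on a correlation the documents do not give: close to nominal at 0.1, about 7–13% of trials at 0.2, and 10–51% at 0.3–0.5. These rates rest on the assumed SDs, on WASO d = 1, and on non-sleep items being unrelated to WASO within arm. The conclusion requires that the HDRS-17 form scores insomnia. It is limited to the WASO path in an exploratory aim.

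**What to change.** In the Aim 3 text of Section 9:

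1. Name the depression outcome, and confirm from the HDRS-17 form which items score sleep.
2. For the WASO mediation model, and for any PLS-SEM path from sleep to depression, prespecify the HDRS-17 without its sleep items alongside the full total. Use PROMIS-Depression as a second outcome, after checking its form for sleep content as well.
3. Interpret WASO as mediating mood improvement only if the score without sleep items supports it.
4. Add a sensitivity analysis using the SSS and RASS data. Removing items does not deal with sedation that affects other ratings.

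The cost is SAP wording and some rescoring; no new data are needed. The reduced score is non-standard and narrower than global severity, so the full total is still reported. The change is best made before unblinding.

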3. GENERAL DESCRIPTION OF STUDY DESIGN

We propose a mechanistic trial enrolling up to 80 perimenopausal women with depression to complete an exALLO (as brexanolone) vs. placebo (saline) infusion using a 1:1 double-blind randomized design (n=up to 40/arm). This trial will be paired with data collection at screening, before (baseline) and following inpatient admission and infusion (4-day, acute effects), and at a 30-day follow-up to assess durability of ALLO effects.

Study participation will last approximately 5 weeks. Participants will undergo behavioral assessments and MRI scans to capture the impact of exALLO vs. placebo on key RdoC constructs thought to underlie depression (Aim 1). Blood will be drawn and optional MRS sequences from MRI scans will be used to measure the impact of exALLO vs. placebo on neuroprotective and pro-inflammatory biomarkers to assay key physiological and molecular mechanisms underlying ALLO's effect on depression (Aim 2). In addition, EEG sleep studies will be obtained to capture the acute effect of exALLO vs. placebo on physiological EEG measures of sleep continuity (Aim 2). Aim 3 analyses will integrate data collected in Aims 1 and 2 with measures characterizing each participant's prior course of depression and Peri status to identify mediators and moderators of ALLO effects on depression.

